10.1 Analysis sets

10.1.1 Full Analysis Set

The Full Analysis Set (FAS) comprises all patients to whom study treatment has been assigned. Patients will be analyzed according to the treatment they have been assigned to.

10.1.2 Safety Set

The Safety Set includes all patients who received at least one dose of study medication. Patients will be analyzed according to the study treatment (regimen) they actually received.

A precise definition of “actually received” will be added in the RAP.

10.1.3 Per-Protocol Set

The Per-Protocol Set (PPS) consists of a subset of the patients in the FAS who are compliant with requirements of the CSP. The PPS may be analysed in case a substantial number of patients was not compliant with requirements of the CSP.

Oncology standards for protocol deviations **potentially** leading to exclusion from the PPS are

- type of indication different from those required by the CSP (e.g., incorrect histology/cytology, not refractory, not metastatic, different grade of cancer, etc.)
- if prior therapy does not match with CSP requirements in terms of number and types of previous therapy regimens
- missing or incomplete documentation of stage of disease (as required in the CSP)
- if ECOG performance status at least 1 category worse than protocol-defined inclusion criteria
- another anti-neoplastic therapy administered after start of study treatment and prior to first tumor assessment

10.2 Patient demographics/other baseline characteristics

Demographic and other baseline characteristics will be summarized for the Full Analysis Set (FAS). Baseline characteristics include prior medication, past/current medical conditions and disease history. Categorical variables will be summarized by absolute and relative frequencies. Continuous variables will be summarized by descriptive statistics (number of valid and missing observations, mean, standard deviation, minimum, median

and maximum, 25th and 75th percentiles). Time-to-event data including rates of affected patients will be assessed using the Kaplan-Meier method.

10.3 Treatments (study treatment, concomitant therapies, compliance)

Duration (days) of drug exposure will be summarized using descriptive statistics separately for ribociclib, letrozole (or goserelin), respectively. Duration of drug exposure will be calculated as the difference between the last and first day of drug application +1. Dosage averages will be calculated including and excluding zero doses for periods of temporary interruption of treatment regardless of whether this was due to safety reasons or patients' non-compliance. Average daily dose levels will be summarized descriptively. Frequencies of the number of patients with any dose reduction (including temporary dose interruption) as well as the number of dose reductions by reason will be given. These analyses will be performed for the safety set.

Concomitant medications and significant non-drug therapies prior to and after the start of the study drug will be coded according to the WHO Drug Reference List and summarized by ATC class and preferred term using frequency distributions.

10.4 Primary objective

The primary objective of this study is the assessment of the clinical benefit rate for the total population and for cohorts A and B separately:

- To assess the clinical benefit rate (CBR) after 24 weeks for ribociclib (LEE011) in combination with letrozole among postmenopausal women and men with hormone receptor positive, HER2- negative, advanced breast cancer who received no prior treatment for advanced disease(Cohort A).
- To assess the clinical benefit rate (CBR) after 24 weeks for ribociclib (LEE011) in combination with letrozole and goserelin among pre-, and perimenopausal women who received no prior treatment for advanced disease as well as pre-, peri- and postmenopausal women and men with hormone receptor positive, HER2- negative, advanced breast cancer who received no more than 1 prior chemotherapy and 2 prior lines of endocrine therapy for advanced disease (Cohort B).

10.4.1 Variable

The **Clinical Benefit Rate (CBR)** is the proportion of patients with a best overall response of confirmed complete (CR) or partial (PR) response or stable disease (SD) or non-complete response, non-progressive disease (NCRNPD) by Week 24. The best overall response for each patient is determined from the sequence of investigator overall lesion responses according to RECIST 1.1. To be assigned a best overall response of CR at least two determinations of CR at least 4 weeks apart before progression are required. To be assigned a best overall response of PR at least two determinations of PR or better at least 4 weeks apart before progression (and not qualifying for a CR) are required. To be assigned a stable disease, two determinations of SD at least 12 weeks apart (and not qualifying for PR or PD) are required.

For further details, please refer to Appendix 14-2: Guidelines for Response, Duration of Overall Response, TTF, TTP, Progression-Free Survival and Overall Survival (based on RECIST 1.1).

10.4.2 Statistical hypothesis, model, and method of analysis

In this single-arm trial, the primary objective is to estimate the CBR. Therefore, no statistical hypothesis or model is underlying the analysis.

The CBR (best overall response of CR or PR or SD or NCRNPD) as well as individual response categories (CR, PR, SD, PD, NCRNPD or unknown) will be summarized using frequency tables together with their associated two-sided exact 95% confidence intervals (Clopper-Pearson method). The Full Analysis Set will be used for the primary efficacy analysis.

10.4.3 Handling of missing values/censoring/discontinuations

Since the definition of the primary variable is derived from tumor assessments based on RECIST 1.1 criteria, these criteria apply for the handling of missing values in tumor assessments. The evaluation of overall lesion response at each assessment is a composite of the target lesion response, non-target lesion response and presence of new lesions (see Post-text supplement 1). If the evaluation of any of the target or non-target lesions identified at baseline could not be made during follow-up, the overall status must be 'unknown' unless progression was seen. Patients with a best overall response assessment of unknown (UNK) will not be regarded as 'responders' but will be included in the denominator for the calculation of the ORR for the FAS.

10.4.4 Supportive analyses

CBR by Week 24 will be additionally presented for the Per-protocol Set. Furthermore, the CBR may be summarized by subgroups for the FAS and PP set, respectively.

10.5 Secondary objectives

10.5.1 Efficacy (secondary)

The following secondary efficacy variables will be analyzed in an explorative manner for the full analysis set (FAS): CBR subgroups, ORR by Week 24, Progression-free survival (PFS) and overall survival (OS).

CBR Subgroups

- To assess the clinical benefit rate (CBR) after 24 weeks for ribociclib (LEE011) in combination with letrozole and goserelin among pre- and perimenopausal women who received no prior treatment for advanced disease.
- To assess the clinical benefit rate (CBR) after 24 weeks for ribociclib (LEE011) in combination with letrozole (and goserelin) among pre-, peri- and postmenopausal women and men who received prior treatment for advanced disease.

ORR by Week 24

The ORR by Week 24 will be derived from the sequence of overall lesion responses as described for the primary efficacy variable. The ORR by Week 24 will be summarized using frequency tables presenting absolute and relative frequencies together with appropriate confidence intervals.

Progression-free survival

Progression-free survival (PFS) is the time from date of start of treatment to the date of event defined as the first documented progression or death due to any cause. If a patient has not had an event, progression-free survival is censored at the date of last adequate tumor assessment. Disease progression for primary efficacy endpoint derivation will be assessed using the local (treating center's radiologist's) investigator's tumor assessment. PFS will be summarized using the Kaplan-Meier method. Percentiles (25%, median, 75%) of the event time distribution will be presented along with their two-sided 95% confidence interval. Additionally, Kaplan-Meier estimates for the proportions of patients progression-free by Week 48 and Week 72 will be presented. The Kaplan-Meier curve will be displayed graphically.

Overall survival

Overall survival (OS) is defined as the time from date of start of treatment to date of death due to any cause. If a patient is not known to have died, survival will be censored at the date of last contact. OS will be summarized using the Kaplan-Meier method as described above. The Kaplan-Meier curve will be displayed graphically. Additionally, the proportion of patients alive at 48 and 96 weeks will be presented

10.5.2 Safety objectives

10.5.2.1 Analysis set and grouping for the analyses

The assessment of safety will be based mainly on the frequency of adverse events and on the number of laboratory values that fall outside of pre-determined ranges. Other safety data (e.g. vital signs, and special tests) will be considered as appropriate. For all safety analyses, the safety set will be used.

All listings and tables will be presented by pretreatment group (postmenopausal patients without prior treatment for advanced disease, pre- and perimenopausal patients without prior treatment for advanced disease and pre-, peri and postmenopausal patients with prior treatment for advanced disease).

The overall observation period will be divided into three mutually exclusive segments:

1. pre-treatment period: from day of patient's informed consent to the day before first dose of study medication
2. on-treatment period: from day of first dose of study medication to 30 days after last dose of study medication
3. post-treatment period: starting at day 30+1 after last dose of study medication.

10.5.2.2 Adverse events (AEs)

Summary tables for adverse events (AEs) have to include only AEs that started or worsened during the on-treatment period, the **treatment-emergent** AEs. However, all safety data (including those from the pre and post-treatment periods) will be listed and those collected during the pre-treatment and post-treatment period are to be flagged.

The incidence of treatment-emergent adverse events (new or worsening from baseline) will be summarized by system organ class and or preferred term, severity (based on CTCAE grades), type of adverse event, relation to study treatment by pretreatment group.

Deaths reportable as SAEs and non-fatal serious adverse events will be listed by patient and tabulated by type of adverse event.

Data collected by AE CRFs will be coded using the MedDRA dictionary. The incidence of treatment-emergent adverse events (new or worsening from baseline) will be summarized by MedDRA system organ class and preferred term using frequency distributions. Additionally, AE will be summarized by maximum severity (based on CTCAE grades), and for AE with suspected drug relation, serious AE (SAE), and AE leading to permanent discontinuation of study drug. All information pertaining to AE noted during the study will be listed by patient, detailing the verbatim term given by the investigator, MedDRA preferred term and system organ class, start/end dates, severity, seriousness, relationship to study drug and action taken. The AE onset will also be shown relative (in number of days) to the date of initial dose.

10.5.2.3 Laboratory abnormalities

Normal laboratory values will not be documented in the CRF. Abnormal laboratory parameters that induce clinical signs or symptoms, require therapy (e.g. hematologic abnormality that requires transfusion or hematological stem cell support), or require changes in study drug(s) constitute an adverse event (Section 8.1.2), must be recorded on the Adverse Events CRF and are coded and summarized accordingly as described in 10.5.2.2.

For laboratory tests covered by the Common Terminology Criteria for Adverse Events (CTCAE) version 4.03, the study's biostatistical and reporting team will grade laboratory data accordingly. For laboratory tests covered by CTCAE, a Grade 0 will be assigned for all non-missing values not graded as 1 or higher. Grade 5 will not be used.

For laboratory tests where grades are not defined by CTCAE, results will be graded by the low/normal/high classifications based on laboratory normal ranges.

10.5.2.4 Other safety data

Data from other tests (e.g., electrocardiogram or vital signs) will be summarized descriptively as appropriate. Notable values will be flagged, and any other information collected will be listed as appropriate.

ECG

ECG results will be reported only if the criteria for SAE are met.

Vital signs

Definitions of notably abnormal results have to part of the CDP, MAP, CSP and RAP.

- shift table baseline to worst on-treatment result
- table with descriptive statistics at baseline, one or several post-baseline time points and change from baseline to this/these post-baseline time points.

ECOG Performance Status

The ECOG Performance Status will be summarized using frequency distributions by visit. Shifts from baseline value to worst post-baseline value will be summarized using frequency distributions.

10.5.3 Biomarkers

Since this clinical trial was not designed to address specific biomarkers-related hypotheses, the analysis of this data should be viewed as exploratory and hypotheses generating.

10.5.3.1 Outline of the data analysis

Additional analyses that may be performed after the completion of the end-of-study CSR will be documented in separate reports. These analyses may include but are not limited to the meta-analysis of data from this study combined with data from other studies or the analysis of biomarkers generated from samples collected during the study but analyzed after the database lock and completion of the CSR. The data analysis will be described in an addendum of the analysis plan or in a stand-alone analysis plan document, as appropriate.

10.5.3.2 Data handling principles

Immunohistochemistry (IHC) data reported from the lab will include quantitative data such as percent tumor and percent positive cells or a semi quantitative measure of protein expression in cellular compartments (i.e. cytoplasm, nucleus, membrane). The pathologist determines whether the staining in a cellular compartment is absent (0+), slight (1+), moderate (2+), or strong (3+).

10.5.3.3 Data analysis principles

[figure not shown]
[figure not shown]
10.5.3.3.1 Analysis sets

The standard analysis sets will be used according to the purpose of a given analysis (e.g. FAS to describe biomarkers, safety/per-protocol set to assess the relationship between biomarkers and selected safety/efficacy endpoints). The number of patients included in a

given analysis will reflect the number of patients in the chosen analysis set which have a valid biomarker assessment.

10.5.3.3.2 Analysis methods

Tumor tissue samples and blood samples will be collected in this trial

10.5.4 Patient-reported outcomes

Health-related quality of life (HRQoL) will be assessed using the EORTC QLQ-C30 and BR23 questionnaires. Scoring will follow the instructions of the respective manuals.

Descriptive statistics will be used to summarize the individual item and scored sub-scale scores of QoL data at each scheduled assessment time point. Patients will be included if they completed at least one questionnaire item. Additionally, change from baseline in the domain scores at the time of each assessment will be summarized. Patients with an evaluable baseline score and at least one evaluable post-baseline score during the treatment period will be included in the change from baseline analyses (assessments after disease progression will be excluded).

10.6 Exploratory objectives

10.7 Interim analysis

Three interim analyses are planned during the study. The first interim analysis will be conducted one year after the first patient has been enrolled and include a preliminary analysis on safety. The second interim analysis will be conducted 12 months after LPFV in the 30% pretreated and premenopausal cohort and will include a preliminary analysis on safety, efficacy and quality of life. The third interim analysis will take place 6 months after the last patient has been recruited and will include a preliminary analysis on safety and efficacy.

10.8 Sample size calculation

Sample size assumptions in this study for postmenopausal patients without prior treatment for advanced disease are based on the data from the CLEE011X2107 study (Juric, poster presented at ASCO 2016), which enrolled a similar patient population.

Regarding patients in later than first lines and pretreated premenopausal patients, assumptions are based on Cristofanilli et al 2016 - PALOMA-3 final analysis.

It is expected that the CBR (based on local assessment) by week 24 is in a range as reported for the CLEE011X2107 study for the ribociclib + letrozole group (CBR = 79%, 95% confidence interval [59% to 92%]).

Using the lower limit of the CI (59%) as a pessimistic estimate for the CBR by week 24, a sample size of 500 produces a two-sided 95% confidence interval with a width equal to 8.6 percentage points (the associated 95% CI is [54.7% to 63.3%]). When using the same CBR as observed (CBR 79%), a sample size of 500 produces a two-sided 95% confidence interval with a width equal to 7.2 percentage points (the 95% CI is [75.4% to 82.6%]). Using the upper limit of the CI (92%) as an optimistic estimate for the CBR, a sample size of 500 produces a two-sided 95% confidence interval with a width equal to 4.8 percentage points (the 95% CI is 89.6% to 94.4%). Assuming an estimated rate of 70% to be recruited in the subgroup of postmenopausal first line patients resulting in a sample size of 350 patients, the width of the confidence interval will be between 10.4 percentage points (pessimistic scenario) and 5.6 percentage points (optimistic scenario).

Regarding the subgroup of second or further treatment lines and premenopausal patients, assuming an estimated rate of 30% to be recruited, and further based on the data as presented by Cristofanili et al. (CBR 67%, 95% CI [61.3% to 71.5%]), the resulting precision based on 150 patients leads to a width of the resulting 95% confidence interval between 15.6 percentage points (pessimistic scenario) and 14.4 percentage points (optimistic scenario). Thus, a sample size of 500 patients allows estimating the CBR in this patient population with reasonable precision.

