	All Pts (N=28)	Pts With Measurable Disease (n=24)
Best overall response, n (%)		
CR	1(4)	1 (4)
PR	10 (36)	10 (42)
SD	10 (36)	10 (42)
PD	3 (11)	3 (13)
NCRNPD	4 (14)	-
Objective response rate (confirmed CR + PR), % (95% CI)	39 (22-59)	46 (26-67)
Disease control rate (confirmed CR + PR + SD + NCRNPD), % (95% CI)	89 (72-98)	88 (68-97)
Clinical benefit rate (confirmed CR + PR + SD >24 weeks + NCRNPD >24 weeks), % (95% CI)	79 (59-92)	79 (58-93)

CI, confidence interval; CR, complete response; NCRNPD, neither complete response nor progressive disease (non-measurable disease); PD, progressive disease; PR, partial response; pts, patients; SD, stable disease.
Data cut-off: October 30, 2015.

In summary, ribociclib in combination with letrozole demonstrated encouraging clinical activity, particularly in the ongoing treatment-naïve group (46% objective response rate, 88% disease control rate, 79% clinical benefit rate in pts with measurable disease). The combination of ribociclib and letrozole has an acceptable safety profile in pts with ERpos, HER2neg aBC. Neutropenia observed with ribociclib is an on-target, antiproliferative side effect of CDK4/6 inhibition. AEs were generally tolerable and managed through dose reductions and interruptions. (Juric et al. Presented at ASCO Annual Meeting, Chicago, IL,

3–7 June 2016, Abstract 568; Munster et al. presented at SABCS, San Antonio, TX, 6–10 December 2016, Abstract P-4-22-18).

Additionally, the ongoing Phase III MONALEESA-2 study (CLEE011A2301) of ribociclib in combination with letrozole for the first-line treatment of postmenopausal women with HR+, HER2-negative advanced (metastatic or loco regionally recurrent) breast cancer, which has completed enrollment (NCT01958021), met its primary endpoint early at the preplanned interim analysis.. Data analysis has been completed and data have been published in October 2016:

Ribociclib in combination with letrozole demonstrated statistically significant benefit over placebo in combination with letrozole in prolonging PFS based on Investigator assessment. Clinical benefit was evident relative to placebo plus letrozole with a 44.4% estimated risk reduction in the primary PFS endpoint as per Investigator assessment (HR=0.556, 95% CI: 0.429, 0.720; $p=3.29\times 10^{-6}$).

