4.1 Description of study design

This is a national, multi-center, open-label, phase IIIb trial to determine the efficacy and safety of treatment with ribociclib (LEE011) plus letrozole in patients with HR+, HER2-negative advanced (recurrent or metastatic) breast cancer.

In this trial a total of 500 patients from approx. 100 centers will be recruited.

Figure 4-1 Study design

The study is sub-divided in the following periods:

Once the Patient Informed Consent Form has been signed and eligibility is confirmed (all inclusion/exclusion criteria have been verified), the patient can be enrolled. All screening evaluations should be performed within 21 days prior to treatment Day 1.

Patients will be treated with daily doses of 600 mg ribociclib (3-weeks-on/1-week-off schedule) in combination with 2.5 mg letrozole daily (continuous dosing). Dose adjustments (dose reduction or interruption) according to safety findings will be allowed. During the study, visits will be performed at baseline, cycle 1 on day 1 & 15 and cycles 2-EOT on day 1. Study treatment will continue until progression, unacceptable toxicity, withdrawal of consent or 80 weeks after the last patient has been enrolled in the trial, whichever comes first.

Novartis will provide ribociclib and letrozole (and goserelin for premenopausal patients) for all patients who are enrolled prior to commercial availability of ribociclib. For patients enrolled afterwards within the approved indication according to SmPC, the investigator will prescribe both ribociclib and letrozole after evaluation of the individual medical patient need for the treatment with ribociclib and letrozole. Patients who are enrolled outside of the label according to SmPC will be provided with study drug by Novartis (i.e. patients in cohort B).

Further treatment after progression will be at the investigator's discretion. Tumor evaluations through CT will be performed for Screening and every 12 weeks during the

study as well as for End of treatment, in case progression as measured by CT was not the reason for end of the treatment.

Patients will be followed up for safety for 30 days after the last dose of study drug. AEs/SAEs with a suspected causality to the study drug must be reported beyond this 30 days safety interval.

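### The total-population interval widths use first-line benefit rates for all 500 patients, although the same section gives 30% of them a lower rate; the optimistic width of 4.8 points cannot occur on those assumptions

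*Protocol*

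**What the plan says.** The total sample is 500: "In this trial a total of 500 patients from approx. 100 centers will be recruited". Protocol 10.4 makes the CBR of the total population part of the primary objective, beside cohorts A and B.

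Protocol 10.8 sets a separate assumption for each cohort.

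- Cohort A: "Sample size assumptions in this study for postmenopausal patients without prior treatment for advanced disease are based on the data from the CLEE011X2107 study". The rate is "CBR = 79%, 95% confidence interval [59% to 92"%]. Table 1-4 in Protocol 1.2.6 shows the same figures for the 28 patients of the treatment-naïve group. The share is fixed here: "Assuming an estimated rate of 70% to be recruited in the subgroup of postmenopausal first line patients resulting in a sample size of 350 patients".
- Cohort B (later lines and premenopausal patients): 30%, or 150 patients, with "CBR 67%, 95% CI [61.3% to 71.5"%].

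The widths for the whole trial are nevertheless calculated at 59%, 79% and 92%. For the middle scenario, "a sample size of 500 produces a two-sided 95% confidence interval with a width equal to 7.2 percentage points"; for the optimistic one, "a sample size of 500 produces a two-sided 95% confidence interval with a width equal to 4.8 percentage points". No mixed rate for the total population is given. SAP 3 repeats the same text and figures.

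**The concern.** The section treats the total population as if it were all cohort A, and a few lines later plans nearly a third of it at a lower rate. Both cannot hold. Because the total-population CBR is a primary estimate, these widths are the planned precision of a primary result.

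The practical risk lies in how the result is read. The section leaves 79% as the apparent planning value for the total, with a stated interval of 75.4% to 82.6%. The cohort assumptions themselves predict 75.4%, which is the lower limit of that interval. A total CBR near 75% could then look like a shortfall when it is what the plan implied.

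**Working it through.** **Inputs** (Protocol 10.8, same in SAP 3): N = 500; cohort A 70% (350) at 59 / 79 / 92%; cohort B 30% (150) at 61.3 / 67 / 71.5%; two-sided 95%, z = 1.96.

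**Step 1: reproduce the stated figures.** Wald width = 2 × 1.96 × √(p(1−p)/n). The section's figures match when the half-width is rounded to 0.1 point and then doubled.

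| n | p | Wald width | Half-width rounded, doubled | Stated |
|---|---|---|---|---|
| 500 | 59% | 8.62 | 8.6 | 8.6 |
| 500 | 79% | 7.14 | 7.2 | 7.2 |
| 500 | 92% | 4.76 | 4.8 | 4.8 |
| 350 | 59% | 10.31 | 10.4 | 10.4 |
| 350 | 92% | 5.68 | 5.6 | 5.6 |
| 150 | 61.3% | 15.59 | 15.6 | 15.6 |
| 150 | 71.5% | 14.45 | 14.4 | 14.4 |

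All seven reproduce. The formula is applied correctly; the question is which rate belongs to the 500.

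**Step 2: mixed rate for the total**, p = 0.7 × p_A + 0.3 × p_B.

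- Pessimistic: 0.7 × 59 + 0.3 × 61.3 = 59.7%
- Expected: 0.7 × 79 + 0.3 × 67 = 75.4%
- Optimistic: 0.7 × 92 + 0.3 × 71.5 = 85.9% (85.85)

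**Step 3: widths at the mixed rate, N = 500.**

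| Scenario | Stated | Wald, mixed | Clopper-Pearson at the section's rate | Clopper-Pearson, mixed |
|---|---|---|---|---|
| Pessimistic | 8.6 | 8.60 | 8.80 | 8.78 |
| Expected | 7.2 | 7.55 | 7.33 | 7.73 |
| Optimistic | 4.8 | 6.11 | 4.96 | 6.31 |

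The Wald intervals are 55.4 to 64.0%, 71.6 to 79.2% and 82.8 to 88.9%. To one decimal the unrounded widths are 8.6, 7.5 and 6.1. If the half-width is rounded first, as in the section, they print as 8.6, 7.6 and 6.2.

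**Step 4: size of the gap, one method at a time.** Optimistic: 6.11/4.76 = 1.28 by Wald and 6.31/4.96 = 1.27 by Clopper-Pearson, so 27 to 28% wider. Expected: 7.55 − 7.14 = 0.41 point. Pessimistic: none beyond rounding.

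**Step 5: can the stated rates occur?** The cohort A rate needed for a given total is (p − 0.3 × p_B)/0.7.

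- Total 92%: with B at 71.5%, (0.92 − 0.2145)/0.7 = 100.8%; with B at 67%, 102.7%. Neither is possible. Even with A at 100% and B at 71.5% the total is 91.45% and the Wald width 4.90.
- Total 79%: with B at 61.3, 67 and 71.5%, A must be 86.6, 84.1 and 82.2%. All three lie within the plan's 59 to 92% for cohort A.

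**Step 6: sensitivity.** With A at 79% and B anywhere from 61.3 to 71.5%, the Wald width runs from 7.72 to 7.41. With A at 92% and B at 67%, the total is 84.5% and the width 6.34. A variance stratified by cohort gives 8.60, 7.49 and 5.88, so the direction does not depend on the method.

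**The case against.** The strongest defence is that the effect on the trial is small. The study estimates a rate with no hypothesis test (Protocol 10.4.2), and no decision rule in the documents depends on a width. The least favourable width, 8.6, is unchanged, and the mixed expected width of 7.55 lies inside the stated range of 4.8 to 8.6. The cohort-specific widths are not touched, and enrollment is complete according to the Amendment 4 rationale. All of this stands, and it limits the point to a correction of the record.

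Several stronger readings are tempting but not supported.

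- *The 7.2 figure is unattainable too.* It is not: cohort A at about 82 to 87% would give a total of 79%. What can be said is that 7.2 is not what the point estimates of 79% and 67% give.
- *The calculation is wrong.* Every stated width follows from its stated rate. The inconsistency is between assumptions.
- *All three widths are too narrow.* The pessimistic width rises to 8.8 only on changing from Wald to Clopper-Pearson, which gives 8.80 at 59% already. Setting a Clopper-Pearson 6.3 against the stated Wald 4.8 also mixes the two effects and inflates the ratio.
- *Cohort B may do far worse than 67%.* Protocol 1.2.6 reports that 32% of 19 previously treated patients received at least 6 cycles. That is treatment duration, not a benefit rate. Cohort B also includes untreated pre- and perimenopausal women, and a different rate would say nothing about the plan's own assumptions.

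**Conclusion.** The point holds for the total-population figures in Protocol 10.8 and SAP 3. The optimistic scenario is excluded by the section's own cohort B range; on the section's mix it is 85.9% with a Wald width of 6.1 points. Seen the other way, the stated width is about 21 to 22% below the one that fits (4.8 or 4.76 against 6.11). The expected scenario is 75.4% with a width of 7.5, a minor difference. The pessimistic scenario is unaffected.

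This rests on the planned 70/30 split, on pairing lower with lower and upper with upper cohort rates, and on the simple binomial interval that the section uses. A reader might infer that the trial is too small or that its precision claim fails. The documents do not support that: the widest total-population interval is still 8.6 points by the section's method, so N and the conclusion of reasonable precision stand.

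**What to change.** In Protocol 10.8 and SAP 3, define the total-population rate in each scenario as 0.7 × cohort A rate + 0.3 × cohort B rate. State 59.7%, 75.4% and 85.9% with Wald widths of 8.6, 7.5 and 6.1 points, and replace the three stated intervals to match. Round in one consistent way.

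If the sponsor prefers the Clopper-Pearson method planned for the analysis (Protocol 10.4.2, SAP 2.5.2), the totals become 8.8, 7.7 and 6.3. The text should then name the method and restate the cohort widths by it as well: about 10.6 to 6.0 points for n = 350 and about 16.1 to 15.0 for n = 150.

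The cost is a text edit in two documents and less favourable optimistic and expected figures. Sample size, analysis and conduct do not change.
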